## INTERVENTION PROTOCOL

From the following scheme (Scheme 3), each training session of the muscle strengthening program was structured for each of the intervention groups, which was based on the principles of training and the Earl and Hoch protocol described in the theoretical framework.

*Scheme 3: A y B Strengthening Program*

After the adjustments described in the pilot test, the strengthening program was applied to the forty patients who were previously randomized to the intervention protocols for groups A and B.

Each of the exercise sessions lasted approximately 45 to 60 minutes, of which, the first 8 to 10 minutes were dedicated to the initial warm-up exercises, the same for program A and B, which gave way to the phase central to the session, that is to say the strengthening exercises: group B took about five minutes less to complete it, because they performed an exercise less than group A in each of the three phases set out in the program; This phase of strengthening lasted approximately 20 to 30 minutes of the total session.

Each session was divided into four parts, of which the second part (central strengthening phase) included between 24 and 28 exercises in total, group A and B respectively. In addition to this, the anatomical conditioning phase was carried out in two weeks, in which 5 to 6 strengthening exercises were prescribed depending on the treatment group, but for both groups the volume was two sets of 10 repetitions, with approximately 30 seconds rest between sets and between exercises, with an execution speed of 1/1 (concentric / eccentric contraction ratio) that allowed patients to adapt to adequate movement control and therefore, joint protection.

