Later, to evaluate if there were differences between the groups of treatment after the intervention on the variables of interest, deltas were generated from the Kujala test, EVA, number of squats, Q angle, balance, physical activity and core strength. with iron and trunk extension, evaluating normality by means of graphic and numerical methods. For the analysis of the differences of medians between the groups, taking into account that the outcomes did not present a normal distribution, and assuming the assumption of independence of the variables, we proceeded to use the non-parametric Mann-Whitney U test. Finally, through the Wilcoxon test, intragroup differences were evaluated for strength, pain and physical activity components.

The hypothesis tests were presented in two tails with an alpha of 0.05 and all the analyzes were executed with the statistical program STATA version 14.0.

BASELINE:

Study population

Therapeutic Effect of Two Muscle Strengthening Programs in Patients with Patellofemoral Pain Syndrome

Table 5 describes the general characteristics of the study population at baseline. There were no significant differences between the two intervention groups (A and B), which means that the randomization was adequate; however, in the total score of the Kujala test there was a difference of 12.5 points between the groups, with a lower score for group B (53.0), which indicates better core strength for these patients. Finally, the sex variable was defined as categorical and the rest of the variables as continuous, for which the medians and their respective interquartile range (IR) are reported, taking into account that the variables did not have a normal distribution.

Table 5: Baseline variables of the study population

Variables	Treatment A (n 20) Medium (RI)	Treatment B (n 20) Medium (RI)	Value p ^a
Sex * (Male, Ref)			
Female	90 (65.7-97.6) *	90.0 (65.7-97.6) *	1,000 ^b
Age	32.5 (25.5-38.0)	29.0 (25.0-36.5)	0,569
Initial weight (Kg)	64.6 (55.3-72.4)	62.7 (52.9-68.5)	0.379
Size (cm)	160 (156.5-167.0)	159.5 (154.0-163.0)	0.423
IMC	25.4 (21.5-27.9)	23.8 (22.3-25.2)	0.456
% of fat	35.4 (28.9-40.4)	35.4 (24.5-38.7)	0,714
% muscle	26.9 (24.5-28.9)	26.2 (24.6-29.0)	0.849
Visceral fat	6 (3.5-7.09)	5 (4.0-6.0)	0.433
IPAQ (minutes)	3003 (1116-4638)	1617 (944-6138)	0,588
Pain	7.5 (5.5-9.0)	7.0 (5.5-8.5)	0.764
Kujala total score	65.5 (42.5-72.5)	53.0 (44.5-71.5)	0,892
Q angle			
Straight	19.0 (15.0-20.0)	18.0 (15.0-20.0)	0,557

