To determine the influence of muscle length (quadriceps, hamstrings, of tensioner of the fascia lata and gastrocnemius) on the alignment of the patella, in **Table 7**, the influence of muscle length on patellar alignment is observed, highlighting that the Right angle Q for people with a positive Ober

Therapeutic Effect of Two Muscle Strengthening Programs in Patients with Patellofemoral Pain Syndrome test (which evaluates the muscle length of tensioner of the fascia lata), obtained an average of 17.26 while for the left Q angle was 18.07 with one and one standard deviation of 3.88 and 4.11 respectively, indicating that those people with decreased muscle length, that is, a positive Ober test, had a higher Q angle compared to those who obtained a negative test. In the same way, a similar effect is observed in the 90-90 test which evaluates the muscle length of the hamstrings, because when the test is negative, that is, there is less muscle retraction, the angle Q is smaller, indicating lesser mal patellofemoral alignment.

Table 7: Influence of muscle length on the alignment of the patella

[figure not shown]
Test	Q angle	
	Straight Half of)	Left Half of)
Ober		
Positive	17.26 (3.88)	18.07 (4.11)
Negative	16.28 (3.51)	16.96 (3.82)
90-90		
Positive	17,02 (3,81)	17,32 (3.90)
Negative	15.0 (0.00)	-
ELY ^a	0.30	0.12
Lunge ^{to}	0.20	-0.08

a: Spearman correlation coefficient

Now, **Figure 5**, highlights the relationship between the muscle length of the quadriceps and the gastrocnemius, measured in degrees and centimeters respectively, and the bilateral Q angle of knees, indicating that there is a positive correlation for both knees in the Ely test, and for the right knee in the Lunge test, this correlation being slight, which suggests that when the muscle length is greater, the angle Q is smaller, whereas for the left knee in the Lunge test, the correlation was negative (-0.08), classified as very mild.

Figure 5: Relationship of muscle length using the Ely and Lunge tests on the bilateral Q angle of the knees.

Therapeutic Effect of Two Muscle Strengthening Programs in Patients with Patellofemoral Pain Syndrome

Source: Author.

Post-Intervention Results

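### Table 7 does not support the SAP's statement that muscle length influences the Q angle: the Ober and 90-90 contrasts have no n, test or interval, and the baseline data are inconclusive

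*SAP*

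**What the plan says.** The SAP section Angle Q and Muscular Length sets out to establish whether the length of four muscle groups affects patellar alignment, and reports that such an influence is seen. Its evidence is the table headed "Table 7: Influence of muscle length on the alignment of the patella".

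- **Ober (tensor fasciae latae).** Patients with a positive test "had a higher Q angle compared to those who obtained a negative test".
- **90-90 (hamstrings).** The text continues that "a similar effect is observed in the 90-90 test which evaluates the muscle length of the hamstrings".
- **Ely (quadriceps) and Lunge (gastrocnemius).** These are given as correlations with the Q angle, which the text calls slight or very mild.

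The table's only statistical footnote, "a: Spearman correlation coefficient", is attached to the Ely and Lunge rows. The Ober and 90-90 rows show what appear to be means with SDs and nothing else. The SAP's Bivariate Analysis section states that "The hypothesis tests were presented in two tails with an alpha of 0.05", but names no test for comparing the Q angle between patients with positive and negative muscle-length tests.

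**The concern.** The SAP gives an affirmative answer to an aim that it states itself, yet a reader cannot judge that answer from what is printed. The Ober differences are small beside the spread. The 90-90 negative cell has an SD of exactly 0.00 on the right and a dash on the left. Without group sizes or intervals, a chance difference and a real one look the same. At stake is a published statement that tight lateral thigh muscles and hamstrings worsen alignment, which others could take as a finding of the trial.

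**Working it through.** **Plan's own figure.** The documents give no p-value, interval or group size for Table 7, so there is nothing to reproduce. The check asks what the printed summaries can support.

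**Inputs (SAP Table 7, right; left).**
- Ober positive 17.26 (3.88); 18.07 (4.11)
- Ober negative 16.28 (3.51); 16.96 (3.82)
- 90-90 positive 17.02 (3.81); 17.32 (3.90)
- 90-90 negative 15.0 (0.00); dash
- Ely 0.30; 0.12
- Lunge 0.20; -0.08

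Total n = 40, from the Protocol: "the strengthening program was applied to the forty patients who were previously randomized". One Q-angle value per patient per side is an assumption.

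**1. Ober, size of the difference.** Right: 17.26 - 16.28 = 0.98. Left: 18.07 - 16.96 = 1.11. The average SD is sqrt((3.88² + 3.51²)/2) = 3.70 right and sqrt((4.11² + 3.82²)/2) = 3.97 left. The standardised differences are 0.98/3.70 = 0.27 and 1.11/3.97 = 0.28.

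**2. Ober, every possible split.** With t = difference / (s_p × sqrt(1/n1 + 1/n2)), and also the Welch form, over all splits of 40 from 2/38 to 38/2, the smallest p is 0.41 (right) and 0.38 (left), both near 20/20. The result therefore does not depend on the missing group sizes.

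**3. Group sizes that best fit the table.** The Ober rows and the 90-90 rows describe the same patients, so their combined mean and SD must agree.
- Left: if all 40 were 90-90 positive, the overall figure is 17.32 (3.90). An Ober split of 13/27 gives (13 × 18.07 + 27 × 16.96)/40 = 17.32, with combined SD 3.90. This matches.
- Right: 38 positive and 2 negative on 90-90 give (38 × 17.02 + 2 × 15.0)/40 = 16.92, SD 3.74. Ober 26/14 gives (26 × 17.26 + 14 × 16.28)/40 = 16.92, SD 3.74. This matches too. One negative gives 16.97 (3.77), against 16.97 (3.76) for 28/12, a poorer match on the SD.

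**4. Ober intervals at those sizes.**
- Right, 26/14: s_p = 3.76, SE = 3.76 × sqrt(1/26 + 1/14) = 1.25, t multiplier 2.024 (38 df). 95% CI 0.98 ± 2.52 = -1.54 to 3.50; p = 0.44 (Welch 0.42).
- Left, 13/27: s_p = 3.91, SE = 3.91 × sqrt(1/13 + 1/27) = 1.32. 95% CI 1.11 ± 2.67 = -1.57 to 3.79; p = 0.41. Welch: -1.70 to 3.92, p = 0.42.

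**5. Power.** Even at 20/20, power for differences of this size is 13% (right) and 14% (left). About 2 × (1.96 + 0.84)² / d², or 224 and 201 per group, would be needed for 80%.

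**6. 90-90.** Right: 17.02 - 15.0 = 2.02. With 38/2 and a pooled SD, the 95% CI is -3.50 to 7.54, p = 0.46. A Welch test gives p of about 0.002, but only because it treats the zero SD of about two equal values as if that group had no variability; this is an artefact. Left: no comparison is possible.

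**7. Ely and Lunge at n = 40.** With t = r × sqrt(38/(1 - r²)) and Fisher z intervals as approximations:

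| Test, side | r | 95% CI | p |
|---|---|---|---|
| Ely right | 0.30 | -0.01 to 0.56 | 0.06 |
| Ely left | 0.12 | -0.20 to 0.42 | 0.46 |
| Lunge right | 0.20 | -0.12 to 0.48 | 0.22 |
| Lunge left | -0.08 | -0.38 to 0.24 | 0.62 |

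The text reads the positive coefficients as longer muscle, smaller angle, without saying which direction of each measurement means a longer muscle.

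**The case against.** The strongest defence is that the sentence about the Ober test is true of the sample: the positive group's mean is higher on both sides. The section claims no statistical significance and describes its correlations modestly. That stands. What fails is the step from sample means to an influence or an effect.

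A second defence is that the claim covers four muscle groups, so two weak rows do not settle it. This is fair, and it is why Ely and Lunge are included above. None reaches 0.05, and only the right-side Ely coefficient comes near.

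Two stronger criticisms of the table are tempting but not supported. A reader might infer that the 90-90 negative group is a single patient. However, a sample SD is undefined for one value, so a printed 0.00 suggests at least two equal values, and two fits the overall SD better. A reader might also take the left-side dash as lost data. Table 6 uses the same mark for categories with no patients, and the left-side figures fit all 40 being positive. The dash is most likely correct reporting; the fault is that the text does not confine its 90-90 remark to the right side.

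Finally, t-type intervals sit uneasily with the SAP's remark on its baseline data, "taking into account that the variables did not have a normal distribution". A rank-based analysis would follow that remark but cannot be run from summary figures.

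**Conclusion.** The statement that muscle length influences patellar alignment is not supported by Table 7. The Ober differences are about a quarter of an SD, with intervals from roughly -1.5 to 3.5 degrees (right) and -1.6 to 3.8 degrees (left), and p is at least 0.38 for any split. The claimed parallel with the 90-90 test has no usable comparison behind it. The Ober conclusion assumes 40 patients with one value per side. The 26/14, 13/27 and 38/2 sizes are inferred from the table, not stated.

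A reader might go further and infer that muscle length has no influence. The documents do not support that either: the upper Ober limits approach one SD and power is low, so the data are inconclusive. Nor does the point weaken the trial's main comparison. This is a secondary, non-randomised look at baseline, and neither the A-versus-B results in Table 8 nor the closing conclusion relies on it.

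**What to change.** In Table 7, print n in every Ober and 90-90 cell. Give the Ober difference with a 95% CI for each side, using a rank-based test and interval if the Q angle is treated as non-normal. Add confidence intervals to the Ely and Lunge coefficients, and say which direction of each measurement means a longer muscle. Delete the inference that the 90-90 test shows the same effect as the Ober test. Replace the statement that an influence is seen with one saying that the baseline data are descriptive and inconclusive on whether muscle length affects the Q angle. The cost is one table revision and one rewritten paragraph, from data already held.

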* Statistical significance p <0.05; a: Chi square test; b: Fisher's exact test

Angle Q and Kujala

Graph 1 shows the correlation between the values of angle Q (right and left) and the total score of the test Kujala obtained in the initial population assessment (baseline), indicating that there is a negative correlation with a coefficient of Spearman's correlation $r = -0.415$ (moderate correlation) for the right Q angle and $r = -0.326$ (slight correlation) for the left Q angle, which means that when the values of the angle Q are greater, the total score in the Kujala test is lower.

Graph 1: Correlation of Q angle values on anterior knee pain with the Kujala test in the baseline.

[figure not shown]

Source: Author.

Angle Q and EVA

In Figure 2 a positive correlation, indicating that as the value of angle Q is greater, the score in the pain measured with a visual analog scale (VAS) is higher for both lower limbs, with a coefficient is observed of Spearman correlation of $r = 0.175$ for the right Q angle and $r = 0.216$ for the left Q angle. It should be noted that although the sample was small, there is a slight correlation.

Graph 2: Correlation of Q angle values on anterior knee pain with EVA in the baseline.

[figure not shown]
Source: Author.

Angle Q - Intervention Groups

In **graphs 3 and 4**, a negative correlation is shown between the values of the angle Q of the right and left knee by treatment groups (A and B) measured at the beginning of the intervention, and the total score obtained in the Kujala test, which indicates that as the angle Q increases, the total Kujala score decreases, with a moderate correlation for group A ($r = -0.545$ right knee) and ($r = -0.548$ left knee) and mild for group B ($r = -0.284$ right knee and $r = -0.173$ left knee).

[figure not shown]
Graph 3: Correlation of the values of the angle Q on the anterior pain of the right knee in the baseline, by treatment groups.

Therapeutic Effect of Two Muscle Strengthening Programs in Patients with Patellofemoral Pain Syndrome

Source: Author.

Graph 4: Correlation of Q angle values on left anterior knee pain in the baseline, by treatment groups.

Source: Author

Angle Q and Muscular Length

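### The SAP reads positive Ely and Lunge correlations as longer muscle, smaller Q angle, against its own label and sign; these and the Q angle–VAS coefficients carry no interval, and all six intervals include zero

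*SAP*

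**What the plan says.** The SAP section Angle Q and Muscular Length asks how muscle length influences patellar alignment. It introduces Figure 5 as showing "the relationship between the muscle length of the quadriceps and the gastrocnemius, measured in degrees and centimeters respectively", set against the Q angle of each knee. The Table 7 rows, right then left, read "ELY ^a 0.30 0.12" and "Lunge ^{to} 0.20 -0.08", with a footnote identifying them as Spearman coefficients. The text describes the signs as "indicating that there is a positive correlation for both knees in the Ely test, and for the right knee in the Lunge test", calls the correlation slight, and concludes "which suggests that when the muscle length is greater, the angle Q is smaller". It sets the left Lunge value (-0.08) apart as negative and very mild.

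Under Angle Q and EVA, the SAP gives coefficients of 0.175 (right) and 0.216 (left) between Q angle and VAS pain, reads them as larger Q angle with more pain, and adds "It should be noted that although the sample was small, there is a slight correlation".

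The Bivariate Analysis section names the Spearman coefficient as the tool for relating two continuous variables. It later states "The hypothesis tests were presented in two tails with an alpha of 0.05". No interval or p-value accompanies any of these coefficients in the text or tables.

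**The concern.** There are two separate problems.

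The first is direction. If the variable is muscle length, a positive coefficient means that a longer muscle goes with a larger Q angle, and the sentence says the opposite. The section set out to answer this very question. The same section reports that shortened muscle on the Ober and 90-90 tests goes with a larger Q angle. Read as labelled, three of the four Ely and Lunge coefficients point the other way, so the printed sentence makes the four muscle tests look more consistent than the numbers show.

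The second is precision. Coefficients between -0.08 and 0.30 are described as relationships, with nothing to tell the reader how far each could be from its printed value. A reader could take it as shown that Q angle tracks quadriceps length, gastrocnemius length and VAS pain.

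**Working it through.** **Direction.** Set side by side, the SAP's own readings are:

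| Section | Pair | Sign of r | Printed reading |
|---|---|---|---|
| Angle Q and Kujala | Q angle, Kujala | negative | larger Q, lower score |
| Angle Q and EVA | Q angle, VAS | positive | larger Q, more pain |
| Angle Q and Muscular Length | Q angle, muscle length (Ely both knees, Lunge right) | positive | longer muscle, smaller Q |

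The first two rows follow the usual convention and the third reverses it. Only left Lunge (-0.08) has the sign that the sentence describes, and the text presents that one as the exception. Neither document says whether a higher reading in degrees or centimetres means a longer or a shorter muscle.

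**Precision.** The coefficients cannot be re-derived without patient data, so the check takes them as printed.

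- *Sample size.* The SAP gives no n for the correlations. The Protocol says "the strengthening program was applied to the forty patients who were previously randomized", and SAP Table 5 shows 20 per group at baseline, so n = 40 is assumed with one value per patient per side. The left-knee means in Table 7 lend some support. With whole-degree angles, all patients 90-90 positive on the left, and truncation allowed, the only fit among totals of 36 to 40 is 13 Ober positive and 27 negative: 235/13 = 18.077, 458/27 = 16.963 and 693/40 = 17.325, against the printed 18.07, 16.96 and 17.32.
- *p-value.* t = r√[(n-2)/(1-r²)] on n-2 = 38 degrees of freedom, two-sided.
- *95% interval.* tanh[atanh(r) ± 1.96/√(n-3)], with 1.96/√37 = 0.322.

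For Ely right, t = 0.30 × √(38/0.91) = 1.94, so p = 0.060. The interval is tanh(0.310 ± 0.322), which is -0.013 to 0.559.

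| Coefficient with Q angle | r | 95% CI | p |
|---|---|---|---|
| Ely right | 0.30 | -0.013 to 0.559 | 0.060 |
| Ely left | 0.12 | -0.199 to 0.416 | 0.46 |
| Lunge right | 0.20 | -0.119 to 0.482 | 0.22 |
| Lunge left | -0.08 | -0.382 to 0.237 | 0.62 |
| VAS right | 0.175 | -0.144 to 0.461 | 0.28 |
| VAS left | 0.216 | -0.102 to 0.494 | 0.18 |

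The smallest |r| that reaches p = 0.05 at n = 40 is 2.024/√(38 + 2.024²) = 0.312. All six fall below it.

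**Sensitivity of the closest case, Ely right.** At the rounding limit r = 0.305, p = 0.056. With the Bonett–Wright standard error √[(1 + r²/2)/(n-3)], the interval is -0.020 to 0.564. At n = 38 and n = 36, p = 0.067 and 0.076. A coefficient of 0.30 would need n = 44 to give p < 0.05.

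**Contrast: overall Q angle with Kujala.** At n = 40 the right coefficient of -0.415 has an interval of -0.643 to -0.119 (p = 0.008), and the left coefficient of -0.326 has -0.579 to -0.016 (p = 0.040). Both exclude zero. The left one depends on n: at n = 36 it would give p = 0.052.

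**The case against.** The strongest reply is that the scoring direction is unstated. If higher Ely degrees and Lunge centimetres mean a shorter muscle, the sentence is correct. The section gives some colour to this: the Ober and 90-90 results are told as reduced length with larger Q angle, and the negative left Lunge is treated as the odd one out, as if positive were the expected sign. This stands to the extent that a reader who infers a proven reversal goes too far. It does not clear the passage, because the variables are labelled as muscle length, no reverse coding is mentioned, and two tests in different units would both have to be reverse-scored.

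Other limits also stand.

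- A reader might infer that the VAS result has the wrong direction too. It does not; those signs are read correctly.
- A reader might infer a departure from the SAP because coefficients lack p-values. The two-tailed statement concerns hypothesis tests, and Spearman is introduced only as a coefficient for evaluating a relationship. No explicit commitment is broken.
- The correlation graphs are not visible in the copy reviewed, so the absence of intervals is established only for the text and tables.
- The SAP hedges: it says slight and very mild, and notes the small sample. Verbal hedging still does not tell the reader that zero lies inside every interval.

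**Conclusion.** The point holds in two parts. First, as labelled, the muscle-length variable, the positive coefficients (0.30, 0.12, 0.20) and the concluding sentence contradict one another. Which of them is wrong depends on a scoring direction that only the investigators can supply. Second, at n = 40 the four muscle-length coefficients and the two Q angle–VAS coefficients all have 95% intervals that include zero. Ely right is borderline (-0.01 to 0.56, p = 0.06); the other five have p from 0.18 to 0.62.

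The second part rests on n = 40 and on large-sample approximations for Spearman's coefficient. For Ely right, the closest case, a smaller n or the wider standard error leaves the conclusion unchanged.

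A reader might infer that no association exists. The data do not show that: the upper limit for Ely right is 0.56, so the estimates are imprecise rather than null. Nor does the point extend to the overall Q angle–Kujala correlations, whose intervals exclude zero at n = 40, or to the Ober and 90-90 comparisons, which are mean differences and a separate matter. These are secondary baseline analyses, and the between-group comparison in Table 8 does not depend on them. The matter is minor.

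**What to change.** 1. State for Ely and Lunge whether a higher reading means a longer or a shorter muscle. If longer, reverse the concluding sentence. If shorter, keep its direction and relabel the variables in the text, Table 7 and Figure 5.
2. Report each Spearman coefficient with its 95% confidence interval and the n used.
3. Reword the Ely, Lunge and Q angle–VAS statements along the lines of: no clear association shown; estimates imprecise. Leave the overall Q angle–Kujala statement and the Ober and 90-90 comparisons outside this rewording.

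The cost is a short re-run on existing data and a few edited sentences. No new data are needed, and the treatment comparison does not change.
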